## 4.2 Exclusion criteria

Patients should not enter the study if any of the following exclusion criteria are fulfilled:

1. Previous IP assignment in the present study.
2. Medical contraindication to etoposide-platinum (carboplatin or cisplatin)-based

chemotherapy.

3. Concurrent enrollment in another clinical study, unless it is an observational (non-interventional) clinical study or during the follow-up period of an interventional study.
4. Received prior systemic therapy for ES-SCLC.
  - Patients who have received prior chemoradiotherapy for limited-stage SCLC must have been treated with curative intent and experienced a treatment-free interval of at least 6 months since last chemotherapy, radiotherapy, or chemoradiotherapy cycle from diagnosis of ES-SCLC
5. Any condition that, in the opinion of the treating physician, would interfere with evaluation of the study drug or interpretation of patient safety.
6. Planned consolidation chest radiation therapy. Radiation therapy outside of the chest for palliative care (ie, bone metastasis) is allowed but must be completed before first dose of the study medication.
7. Major surgical procedure (as defined by the investigator) within 28 days prior to the first dose of IP. Note: Local surgery of isolated lesions for palliative intent is acceptable.
8. History of allogeneic organ transplantation.
9. Has a paraneoplastic syndrome (PNS) of autoimmune nature, requiring systemic treatment (systemic steroids or immunosuppressive agents) or has a clinical symptomatology suggesting worsening of PNS.
10. Active or prior documented autoimmune or inflammatory disorders (including inflammatory bowel disease [eg, colitis or Crohn's disease], diverticulitis with the exception of diverticulosis, systemic lupus erythematosus, sarcoidosis syndrome, or Wegener syndrome [granulomatosis with polyangiitis, Graves' disease, rheumatoid arthritis, hypophysitis, and uveitis, etc]). The following are exceptions to this criterion:
  - Patients with vitiligo or alopecia
  - Patients with hypothyroidism (eg, following Hashimoto syndrome) and stable on hormone replacement
  - Any chronic skin condition that does not require systemic therapy
  - Patients without active disease in the last 5 years may be included but only after consultation with the Study Physician
  - Patients with celiac disease controlled by diet alone
11. Uncontrolled intercurrent illness, including but not limited to, ongoing or active infection, symptomatic congestive heart failure, uncontrolled hypertension, unstable angina pectoris, uncontrolled cardiac arrhythmia, active interstitial lung disease, serious chronic gastrointestinal conditions associated with diarrhea, or psychiatric illness/social situations that would limit compliance with study requirement, substantially increase risk of incurring AEs or compromise the ability of the patient to give written informed consent.
12. History of active primary immunodeficiency.
13. Active infection including tuberculosis (clinical evaluation that includes clinical history, physical examination and radiographic findings, and tuberculosis testing in line with local

practice), hepatitis B (known positive HBV surface antigen [HbsAg] result), hepatitis C, or human immunodeficiency virus (positive HIV 1/2 antibodies). Patients with a past or resolved HBV infection (defined as the presence of hepatitis B core antibody [anti-HBc] and absence of HbsAg) are eligible. Patients positive for hepatitis C virus (HCV) antibody are eligible only if polymerase chain reaction is negative for HCV RNA.

14. Current or prior use of immunosuppressive medication within 14 days before the first dose of durvalumab. The following are exceptions to this criterion:

- Intranasal, inhaled, topical steroids or local steroid injections (eg, intra articular injection).
- Systemic corticosteroids at physiologic doses not to exceed 10 mg/day of prednisone or its equivalent.
- Steroids as premedication for hypersensitivity reactions (eg, CT scan premedication). Premedication with steroids for chemotherapy is acceptable.

15. Receipt of live, attenuated vaccine within 30 days prior to the first dose of IP. Note: Patients, if enrolled, should not receive live vaccine whilst receiving IP and up to 30 days after the last dose of IP.

16. Female patients who are pregnant or breastfeeding or male or female patients of reproductive potential who are not willing to employ effective birth control from Screening to 90 days after the last dose of durvalumab.

For procedures for withdrawal of incorrectly enrolled patients, see Section 4.4.

### **4.3 Patient enrolment**

At Screening (Days -28 to -1), the investigator(s) or suitably trained delegate(s) will perform the following:

1. Obtain signed informed consent from the potential patient before any study-specific procedures are performed.
2. Determine patient eligibility. See Section 4.1 and Section 4.2.
3. Choose platinum agent that the patient would receive in cycle 1 (based on the most appropriate option for the patient).

The above does not list the exact sequence of study related procedures but provides the steps that should be taken during the screening period prior to baseline of the patient.

Patients must not be treated unless all eligibility criteria have been met.

Patients should begin treatment with durvalumab on Day 1 of Cycle 1 of EP.

### **4.4 Procedures for handling incorrectly enrolled**

Patients who fail to meet the eligibility criteria should not, under any circumstances, be enrolled or receive study medication. There can be no exceptions to this rule. Patients who are enrolled but found to not meet all the eligibility criteria must not be initiated on treatment and must be withdrawn from the study as a screen failure.

When a patient does not meet all the eligibility criteria but is incorrectly started on treatment, the investigator should inform the AstraZeneca Study Physician immediately, and the Study Physician and the investigator should discuss whether to continue or discontinue the patient from treatment. The Study Physician must ensure that all decisions are appropriately documented.

#### 4.5 Restrictions

The following restrictions apply while the patient is receiving study treatment and for the specified times before and after:

##### 1. Female patient of childbearing potential

- Females of childbearing potential who are sexually active with a non-sterilized male partner must use at least 1 highly effective method of contraception (Table 1) from the time of Screening and must agree to continue using such precautions for 90 days after the last dose of durvalumab. Non-sterilized male partners of a female patient must use male condom plus spermicide throughout this period. Cessation of birth control after this point should be discussed with a responsible physician. Not engaging in sexual activity for the total duration of the drug treatment and the drug washout period is an acceptable practice; however, periodic abstinence, the rhythm method, and the withdrawal method are not acceptable methods of birth control. Female patients should also refrain from breastfeeding throughout this period.

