#### **4.6 Discontinuation of study treatment**

An individual patient will not receive any further IP (durvalumab + EP or durvalumab monotherapy) if any of the following occur in the patient in question:

- Withdrawal of consent from further treatment with IP. The patient is, at any time, free to discontinue treatment, without prejudice to further treatment. A patient who discontinues treatment is normally expected to continue to participate in the study unless they specifically withdraw their consent to further participation in any study procedures and assessments (see Section 4.7.2).
- An AE that, in the opinion of the investigator or AstraZeneca, contraindicates further dosing.
- An AE that meets criteria for discontinuation of durvalumab as defined in the Dosing Modification and Toxicity Management Guidelines (see section 7.9 and Annex to Protocol).
- Evidence of a new paraneoplastic syndrome(s) or worsening of an existing paraneoplastic

- syndrome(s).
- Pregnancy or intent to become pregnant
  - Noncompliance with the study protocol that, in the opinion of the investigator or AstraZeneca, warrants withdrawal from treatment with IP (eg, refusal to adhere to scheduled visits).
  - Initiation of alternative anticancer therapy including another investigational agent.
  - Clinical progression or confirmed radiological progression per Investigator assessment (refer to Appendix C) and Investigator determination that the patient is no longer benefiting from treatment with IP.
  - EP treatment should be discontinued after a maximum of 6 cycles
  - EP treatment  $\leq$  2 cycles
  - Durvalumab treatment delayed  $>$  12 weeks
- 

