### **7.7.2 Paternal exposure**

Male patients should refrain from fathering a child or donating sperm during the study and for 90 days after the last dose of durvalumab, whichever is the longer time period. Please follow the local prescribing information relating to contraception and the time limit for such precautions for SoC agents.

Pregnancy of the patient's partner is not considered to be an AE. However, the outcome of all pregnancies (spontaneous miscarriage, elective termination, ectopic pregnancy, normal birth, or congenital abnormality) occurring from the date of the first dose until 90 days after the last dose of durvalumab should, if possible, be followed up and documented.

Where a report of pregnancy is received, prior to obtaining information about the pregnancy, the Investigator must obtain the consent of the patient's partner.

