## **7.9 Management of investigational product-related toxicities**

The following guidance should be followed for management of toxicities.

- Treat each of the toxicities with maximum supportive care (including holding the agent suspected of causing the toxicity where required).
- If the symptoms promptly resolve with supportive care, consideration should be given to continuing the same dose of the assigned IP along with appropriate continuing supportive care. If medically appropriate, dose modifications are permitted.
- All dose modifications should be documented with clear reasoning and documentation of the approach taken.
- Patients should be thoroughly evaluated to rule out any alternative etiology (eg, disease progression, concomitant medications, and infections). This includes EP induced toxicity. In the event that toxicities are clearly attributed to chemotherapy, both EP and durvalumab should be delayed.
- In the absence of a clear alternative etiology, all events should be considered potentially immune related and the toxicity management guidelines detailed in the Annex to Protocol should be followed.
- In the event that durvalumab is temporarily discontinued or delayed as part of the toxicity management guidance, EP should still be administered as scheduled; every effort should be made to ensure patients receive at least 4 cycles of EP in the study, if conditions allow.

All toxicities will be graded according to NCI CTCAE, Version 5.0.

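### Women's post-treatment contraception is timed only from the last durvalumab dose, with no end point after chemotherapy, although chemotherapy can outlast durvalumab and men are sent to the label limit for the same drugs

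*Protocol*

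**What the plan says.** Section 4.5 opens by stating that "The following restrictions apply while the patient is receiving study treatment and for the specified times before and after". Under item 1, women of childbearing potential must use a highly effective method from Screening and "must agree to continue using such precautions for 90 days after the last dose of durvalumab". The same item adds: "Cessation of birth control after this point should be discussed with a responsible physician". Exclusion criterion 16 (Section 4.2) bars patients "who are not willing to employ effective birth control from Screening to 90 days after the last dose of durvalumab". Neither place names etoposide, cisplatin or carboplatin.

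EP is nevertheless investigational product. Table 6 lists it, and Section 4.6 reads: "An individual patient will not receive any further IP (durvalumab + EP or durvalumab monotherapy) if any of the following occur". On dosing, Section 7.9 states: "In the event that durvalumab is temporarily discontinued or delayed as part of the toxicity management guidance, EP should still be administered as scheduled", and that "every effort should be made to ensure patients receive at least 4 cycles of EP in the study, if conditions allow".

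For men, Section 7.7.2 (Paternal exposure) gives the same 90 days after durvalumab and then adds: "Please follow the local prescribing information relating to contraception and the time limit for such precautions for SoC agents". Section 7.7.1 (Maternal exposure) has no corresponding sentence.

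**The concern.** The post-treatment clock for women starts from one drug of a regimen that also contains cytotoxics, and the dosing rules let the cytotoxics finish last. Under Section 7.9 a durvalumab hold leaves EP running. Under Section 7.9.2 an EP delay also delays durvalumab. So during chemotherapy a hold of one drug separates the two in one direction only: EP goes on without durvalumab. If durvalumab is then never restarted, for example because of progression or the patient's refusal, the 90 days have been running since before the last cytotoxic dose.

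Section 7.7.2 shows that the protocol does not treat the durvalumab period as settling the matter for the chemotherapy agents, since it sends men to the label as well. The patient who could carry the pregnancy has no such instruction. What is at stake is patient protection in a small group; no endpoint, estimate or analysis is affected.

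**Working it through.** The protocol gives no figure of its own to reproduce. The check counts days on its schedule.

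**Inputs**
- EP every 3 weeks for 4 to 6 cycles (Table 2, note k).
- Durvalumab on Day 1 of each cycle; etoposide on Days 1, 2 and 3 (Section 8.1.1).
- Contraception ends 90 days after the last durvalumab dose (Section 4.5 item 1).
- All investigational product stops if durvalumab is delayed more than 12 weeks (Section 4.6).
- Assumption: EP stays on its 21-day schedule.

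**Formulas**, with n EP cycles and the last durvalumab dose in cycle k:
- Last etoposide day = 1 + 21(n − 1) + 2, which is Day 66, 87 or 108 for n = 4, 5 or 6.
- Last durvalumab day = 1 + 21(k − 1), so required contraception ends on Day 91 + 21(k − 1).
- Days of required contraception after the last etoposide dose = [91 + 21(k − 1)] − [3 + 21(n − 1)] = 88 − 21(n − k).

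| EP cycles given without durvalumab (n − k) | Days left after last etoposide |
|---|---|
| 0 | 88 |
| 1 | 67 |
| 2 | 46 |
| 3 | 25 |
| 4 | 4 (6 on one reading of the 12-week rule) |

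**Does the 12-week stop prevent these cases?** The protocol does not say how the 12 weeks are counted, so both counts are tried.
- *Up to three such cycles.* Counted from the last dose, the earliest limit is Day 85, 106 or 127 for k = 1, 2 or 3. The last etoposide with three such cycles falls on Day 66, 87 or 108. The limit is never reached. With 4 EP cycles these cases are last durvalumab in cycle 3, 2 or 1.
- *Four such cycles* (n = 5, k = 1, or n = 6, k = 2). If the 12 weeks run from the last dose and bar etoposide after that day, the limits are 1 + 84 = Day 85 and 22 + 84 = Day 106, leaving 91 − 85 = 6 and 112 − 106 = 6 days. If they run from the missed dose, the limits are 22 + 84 = Day 106 and 43 + 84 = Day 127. Neither is reached, leaving 91 − 87 = 4 and 112 − 108 = 4 days. Checking the limit only on each Day 1 also gives 4.
- *Five such cycles* (n = 6, k = 1) are possible only if the 12 weeks run from the missed dose, so this case is left out of the size.

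**Shortfall.** If the label asked for L days after the last EP dose, the shortfall would be max(0, L − days left). The protocol gives no L. With three such cycles, for instance, any L above 25 days would not be met.

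**The case against.** The strongest reply is that no harm is shown. The figures are days of cover remaining, all are positive, and without a required post-EP period none is proved too short. That stands, and it is why no shortfall is claimed.

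Second, other provisions narrow the gap. The Section 4.5 lead-in keeps contraception in force throughout EP, and stopping is to be discussed with a physician. The abstinence option runs through drug washout, and Section 8.1.3 has EP given under prescribing information or site guidance. Pregnancy tests run every 3 weeks during chemotherapy and at safety follow-up. These help, but none sets a period after EP. The lead-in covers only treatment itself. The physician discussion has no interval to guide it, and washout is not defined for EP. Section 8.1.3 concerns administration. Tests detect pregnancy rather than prevent it, and the safety visit is itself timed from durvalumab.

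Third, the contrast between the sexes rests on one sentence. Section 4.5 item 2 for men is also timed only from durvalumab, and criterion 16 treats both sexes alike. This is correct, but men are still reached through Section 7.7.2, and women have no equivalent.

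Fourth, the path is narrow. An adverse event meeting the durvalumab discontinuation criteria, or a delay over 12 weeks, ends all investigational product. In the usual course durvalumab outlasts EP. This also stands and limits the grade.

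**Conclusion.** The concern holds, as a minor point. Followed exactly, the rule lets a woman's required contraception end without regard to her last cytotoxic dose, while a male patient is directed to the label limit for the same drugs. Cover after the last etoposide dose falls from 88 days by 21 days per EP cycle given without durvalumab: to 67, 46 and 25 days, and to 4 to 6 days at the extreme.

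This rests on EP keeping its 21-day schedule and on durvalumab being held and never resumed. Only the 4-to-6-day value depends on how the 12-week limit is counted. When durvalumab continues as maintenance after EP, cover runs 90 days beyond the last maintenance dose and the problem does not arise. The number of women of childbearing potential is not given; few are assumed. Confidence is medium, because the required period after EP is not in the protocol.

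**What to change.** In Section 4.5 item 1 and in exclusion criterion 16, run women's contraception to the later of two dates: 90 days after the last durvalumab dose, and the end of the period in the local prescribing information after the last EP dose. This applies to women what Section 7.7.2 already asks of men. For consistency, the sponsor could also cross-refer to the chemotherapy limit in Section 7.7.1 and in Section 4.5 item 2.

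The cost is one clause in each of the two places and matching consent text, with no extra visits or tests. The only downside is longer contraception for a few patients.

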##### 2. Male patients with a female partner of childbearing potential

- Non-sterilized males who are sexually active with a female partner of childbearing potential must use a male condom plus spermicide from Screening through 90 days after receipt of the final dose of durvalumab. Not engaging in sexual activity is an acceptable practice; however, occasional abstinence, the rhythm method, and the withdrawal method are not acceptable methods of contraception. Male patients should refrain from sperm donation throughout this period.
- Female partners (of childbearing potential) of male patients must also use a highly effective method of contraception throughout this period (Table 1).

Note: Females of childbearing potential are defined as those who are not surgically sterile (ie, bilateral tubal ligation, bilateral oophorectomy, or complete hysterectomy) or post-menopausal.

Women will be considered post-menopausal if they have been amenorrheic for 12 months without an alternative medical cause. The following age-specific requirements apply:

- Women <50 years of age would be considered post-menopausal if they have been amenorrheic for 12 months or more following cessation of exogenous hormonal treatments and if they have luteinizing hormone and follicle-stimulating hormone levels in the post-menopausal range for the institution or underwent surgical sterilization (bilateral oophorectomy or hysterectomy).
- Women  $\geq$ 50 years of age would be considered post-menopausal if they have been amenorrheic for 12 months or more following cessation of all exogenous hormonal treatments, had radiation-induced menopause with last menses >1 year ago, had

chemotherapy-induced menopause with last menses >1 year ago, or underwent surgical sterilization (bilateral oophorectomy, bilateral salpingectomy or hysterectomy).

Highly effective methods of contraception, defined as those that result in a low failure rate (ie, less than 1% per year) when used consistently and correctly are described in Table 1. Note that some contraception methods are not considered highly effective (eg, male or female condom with or without spermicide; female cap, diaphragm, or sponge with or without spermicide; non-copper-containing intrauterine device; progestogen-only oral hormonal contraceptive pills where inhibition of ovulation is not the primary mode of action [excluding Cerazette/desogestrel, which is considered highly effective]; and triphasic combined oral contraceptive pills).

**Table 1 Highly effective methods of contraception (<1% failure rate)**

| Barrier/intrauterine methods                                     | Hormonal methods                                    |
|---|--|
| Copper T intrauterine device  | Etonogestrel implants: eg, Implanon or Norplan             |
| Levonorgestrel-releasing intrauterine system (eg, Mirena®) a | Intravaginal device: eg, ethinylestradiol and etonogestrel |
|   | Medroxyprogesterone injection: eg, Depo-Provera            |
|   | Normal and low-dose combined oral contraceptive pill       |
|   | Norelgestromin/ethinylestradiol transdermal system         |
|   | Cerazette (desogestrel)                                    |

a This is also considered a hormonal method.

3. Patients should not donate blood or blood components while Participating in this study and through 90 days after receipt of the final dose of durvalumab or until alternate anticancer therapy is started.
4. Restrictions relating to concomitant medications are described in Section 8.7.

#### **4.6 Discontinuation of study treatment**

An individual patient will not receive any further IP (durvalumab + EP or durvalumab monotherapy) if any of the following occur in the patient in question:

- Withdrawal of consent from further treatment with IP. The patient is, at any time, free to discontinue treatment, without prejudice to further treatment. A patient who discontinues treatment is normally expected to continue to participate in the study unless they specifically withdraw their consent to further participation in any study procedures and assessments (see Section 4.7.2).
- An AE that, in the opinion of the investigator or AstraZeneca, contraindicates further dosing.
- An AE that meets criteria for discontinuation of durvalumab as defined in the Dosing Modification and Toxicity Management Guidelines (see section 7.9 and Annex to Protocol).
- Evidence of a new paraneoplastic syndrome(s) or worsening of an existing paraneoplastic

- syndrome(s).
- Pregnancy or intent to become pregnant
  - Noncompliance with the study protocol that, in the opinion of the investigator or AstraZeneca, warrants withdrawal from treatment with IP (eg, refusal to adhere to scheduled visits).
  - Initiation of alternative anticancer therapy including another investigational agent.
  - Clinical progression or confirmed radiological progression per Investigator assessment (refer to Appendix C) and Investigator determination that the patient is no longer benefiting from treatment with IP.
  - EP treatment should be discontinued after a maximum of 6 cycles
  - EP treatment  $\leq$  2 cycles
  - Durvalumab treatment delayed  $>$  12 weeks
- 

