#### Study design:

This will be an open-label, single-arm, multicenter, Phase IIIb study to determine the safety of durvalumab + etoposide and cisplatin or carboplatin as first-line treatment in patients with extensive stage small-cell lung cancer. Patients who fulfil all the inclusion criteria and none of the exclusion criteria will be enrolled and receive treatment with durvalumab + etoposide and either cisplatin or carboplatin (EP) for 4 to 6 cycles. Durvalumab will be administered at a dose of [REDACTED] with first-line chemotherapy (EP) and will continue to be administered as monotherapy every 4 weeks (Q4W) post-chemotherapy until progressive disease (PD) or intolerable toxicity. Prophylactic cranial irradiation (PCI) is allowed at the investigators' discretion as per SoC guidance for ES-SCLC. Patients will attend a safety follow up visit 90 days after last dose of durvalumab.

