### **Duration of treatment**

Unless specific treatment discontinuation criteria are met, patients enrolled will continue durvalumab therapy until disease progression or intolerable toxicity, as per investigator assessment.

EP will be administered for 4 to 6 cycles for patients per investigator clinical decision.

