### 7.9.2 Chemotherapy

Chemotherapies are associated with a number of unwanted effects. EP-related toxicity management, dose adjustment, including dose delays and reductions should be performed as indicated in the local prescribing information for the relevant agent. In the event of unfavorable tolerability, patients can switch between cisplatin and carboplatin therapy at any point on study (assuming eligibility for the switched therapy is met).

EP is the SoC and is expected to cause hematologic non-immune-related AEs for which the non-immune-related Toxicity Management Guidelines should not be applied. Sites should utilize dose delays, dose modifications, G-CSF or component transfusions (eg, platelet transfusions) as necessary per local standards to maintain the dose and schedule of EP treatment to optimize tolerability for individual patients.

In the event that an AE can reasonably be attributed to EP, dose adjustment of EP should be attempted before modifying the administration of durvalumab.

In the event that EP is delayed, durvalumab should also be delayed and to be resumed as soon as feasible. Every effort should be made to ensure patients receive at least 4 cycles of EP, if conditions allow.

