**8.2.1 Duration of treatment and criteria for treatment through progression**

All treatment will be administered beginning on Day 1.

Treatment with SoC chemotherapy (EP) will be limited to 6 cycles on a Q3W schedule, at the investigators' discretion.

Durvalumab will be administered beginning on Day 1 until PD unless there is unacceptable toxicity, withdrawal of consent, or another discontinuation criterion is met.

During the treatment period, patients who are clinically stable at an initial RECIST 1.1-defined PD may continue to receive study treatment at the discretion of the Investigator and patient as long as they are deemed to be receiving clinical benefit. A follow-up scan is to be collected after the initial RECIST 1.1-defined PD, 4-8 weeks after the prior assessment of PD.

Patients who continue to receive IP at the discretion of the Investigator can receive treatment until they are no longer deemed to be receiving clinical benefit or end of the study, unless there is unacceptable toxicity, withdrawal of consent, or another discontinuation criterion is met. Image acquisitions and tumor assessments should continue on their regular imaging schedule for the duration of treatment.

Patients with rapid tumor progression or with symptomatic progression that requires urgent medical intervention (eg, central nervous system metastasis, respiratory failure due to tumor compression, spinal cord compression) will not be eligible for continuing durvalumab.

For all patients who are treated through progression, the investigator should ensure patients do not have any significant, unacceptable or irreversible toxicities that indicate continuing treatment would not further benefit the patient.

Patients who AstraZeneca and the investigator determine may not continue treatment after PD will be followed up for survival. Patients who have discontinued treatment due to toxicity or symptomatic deterioration, or who have commenced subsequent anticancer therapy, will be followed up until confirmed disease progression and for survival.

Following confirmed disease progression, standard chemotherapy can be offered by the investigator per local practice.

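### Section 4.6 places two chemotherapy cycle counts in a list that ends all study drug, and Sections 7.9 and 7.9.2 differ on holding durvalumab, so who stops or delays durvalumab is ambiguous

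*Protocol*

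**What the plan says.** Protocol Section 4.6 sets the scope of its list in the opening line: "An individual patient will not receive any further IP (durvalumab + EP or durvalumab monotherapy) if any of the following occur". Among consent, adverse-event, pregnancy and progression items it then lists "EP treatment should be discontinued after a maximum of 6 cycles" and, as a bare fragment, "EP treatment $\leq$ 2 cycles". The last item stops treatment when durvalumab has been delayed by more than 12 weeks.

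Other sections give the treatment course. The Synopsis (Duration of treatment) states "EP will be administered for 4 to 6 cycles for patients per investigator clinical decision", and the Synopsis (Study design) says durvalumab "will continue to be administered as monotherapy every 4 weeks (Q4W) post-chemotherapy until progressive disease (PD) or intolerable toxicity". The post-chemotherapy table in Section 8.2 also schedules it Q4W to progression. Section 8.2.1 limits chemotherapy to six cycles and says of durvalumab: "Durvalumab will be administered beginning on Day 1 until PD unless there is unacceptable toxicity, withdrawal of consent, or another discontinuation criterion is met".

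On toxicity due to chemotherapy, Section 7.9 says "In the event that toxicities are clearly attributed to chemotherapy, both EP and durvalumab should be delayed". Section 7.9.2 says "In the event that an AE can reasonably be attributed to EP, dose adjustment of EP should be attempted before modifying the administration of durvalumab". The same section counts both delays and reductions as EP dose adjustment, and adds that durvalumab is delayed whenever EP is delayed.

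**The concern.** A rule for permanent discontinuation has to tell a site which drug stops, for what reason and when. The two cycle-count items do not do this. One names EP only but sits in a list that ends everything. The other has no verb, reason or time point. The two toxicity sections can also give a site different answers on whether to hold durvalumab.

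This is a safety study. Its primary measures are the incidences of Grade 3 or higher adverse events and of immune-mediated adverse events, and Section 9.4.1 includes events in the summaries up to 90 days after durvalumab is discontinued. The date durvalumab stops therefore sets how long each patient is observed for both measures. Treatment discontinuation due to an adverse event is a secondary endpoint, so the recorded reason for stopping matters as well.

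**Working it through.** **1. The plan's own figure.** Section 9.2 gives precision at 300 patients of 5.7% (incidence 60%) and 4.7% (incidence 20%) by Clopper-Pearson. The limits are the 2.5% quantile of Beta(x, n−x+1) and the 97.5% quantile of Beta(x+1, n−x).

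- x = 180, n = 300: 54.21% to 65.59%, half-width (65.59 − 54.21)/2 = 5.69%.
- x = 60, n = 300: 15.62% to 24.98%, half-width (24.98 − 15.62)/2 = 4.68%.

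Both agree with the plan, as do all 15 cells of Table 9. No input depends on the discontinuation rules.

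**2. The Section 4.6 opening line applied to the two items.**

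| Item | Who meets it | Taken with the opening line | Elsewhere |
|---|---|---|---|
| Six-cycle maximum | Only patients given 6 of the permitted 4 to 6 cycles | Durvalumab ends with EP | Synopsis, 8.2, 8.2.1: durvalumab continues to progression |
| Two cycles or fewer | Literally every patient during cycles 1 and 2 | All drug ends in cycle 1 or 2 | Synopsis: 4 to 6 cycles; 7.9 and 7.9.2: every effort to reach at least 4, if conditions allow |

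The two-cycle item may be meant for patients whose EP ends early, but the text does not say whether for toxicity, by choice or for any reason. Sections 7.9 and 7.9.2 allow for fewer than 4 cycles without saying what then happens to durvalumab.

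**3. Whether the cross-references settle it.** Section 8.2.1 makes durvalumab to progression subject to any other discontinuation criterion. Section 7.9.1 names Section 4.6 as a place to find the circumstances for permanent discontinuation. Both lead back to the list in question.

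**4. Section 7.9 against 7.9.2.**

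| EP toxicity managed by | 7.9 | 7.9.2 | Agree? |
|---|---|---|---|
| Delaying EP | Delay both | Durvalumab delayed too | Yes |
| Adjusting EP without delay, for example a reduction | Delay both | Try the EP adjustment before modifying durvalumab | No |

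The inconsistency is confined to the second row. It bears on discontinuation because durvalumab delays count toward the 12-week limit in Section 4.6.

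**5. Observation time.** With 21-day cycles and no delays, the last combination dose after c cycles falls on Day 1 + 21(c − 1), and the summary window closes 90 days later.

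- All drug ends after 2 cycles: Day 1 + 21 = 22; window closes at 22 + 90 = Day 112.
- All drug ends after 6 cycles: Day 1 + 105 = 106; window closes at 106 + 90 = Day 196.
- Durvalumab to progression: no fixed end.

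**6. Illustration of what a shorter window can do.** Assume a constant hazard of immune-mediated events that gives the planning value of 20% by Day T. The incidence by Day 112 is then 1 − 0.8^(112/T).

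- T = 154: 15.0%.
- T = 238: 10.0%.
- T = 330: 7.3%.

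The constant hazard and the values of T are assumptions. The figures describe a group observed only to Day 112 and are not a forecast for the trial.

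**The case against.** The strongest reply is that no sensible site would follow the literal reading. The six-cycle item names EP only, and durvalumab maintenance to progression appears in the Synopsis, the schedule of assessments and Section 8.2. The literal two-cycle reading would stop every patient before the planned minimum of 4 cycles. Much of this stands: a site would probably treat the six-cycle item as an EP cap. It does not rescue the two-cycle item, because rejecting the literal reading still leaves the reason, the time point and the fate of durvalumab unstated.

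A reader might infer more than the documents support:

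- *That the primary endpoint or its exposure is undefined.* Section 9.3.1 fixes the analysis set as everyone with at least one dose, and Section 9.4.1 ties the summary window to the actual end of durvalumab. Both can be computed whatever the reason for stopping.
- *That every patient meets both items.* This is literally true only of the two-cycle item.
- *That Sections 7.9 and 7.9.2 give opposite instructions.* They agree whenever EP is delayed. Their triggers also differ in strength: clear attribution in one, reasonable attribution in the other.
- *That a count of affected patients can be given.* The Protocol states no share for patients receiving six cycles or stopping EP by two, so any count would rest on shares chosen by the reader.

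Some text is not available: the note to the post-chemotherapy table is redacted and the toxicity guideline is a separate annex. Either might clarify intent, but neither changes the wording of Section 4.6.

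**Conclusion.** The point holds as an internal contradiction with a limited consequence. Section 4.6, followed as written, conflicts with the treatment course in the Synopsis and Sections 8.2 and 8.2.1, and its two-cycle item cannot be applied. Sections 7.9 and 7.9.2 are inconsistent where EP toxicity is managed without delay.

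What is left ambiguous is who stops or delays durvalumab, and through that the exposure time, the end of the 90-day window and the treatment-discontinuation data. For an individual patient the literal readings close the window near Day 112 or Day 196, against no fixed end under treatment to progression. Those days assume 21-day cycles without delays. Whether sites would actually differ is a risk that the text creates, not something the documents show. The endpoint definitions, the safety set, the 300 patients and the stated precision are unaffected. It should be corrected because a permanent-stop rule should not depend on a site's guess at its meaning.

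**What to change.** Amend the wording in three places, with the clinical team deciding the content:

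1. Reconcile Section 4.6 with the Synopsis and Sections 8.2 and 8.2.1 by separating criteria that end EP only from criteria that end all study drug.
2. Complete the two-cycle item: state what it refers to, for which reason and at which time point, and what it means for durvalumab.
3. Reconcile Sections 7.9 and 7.9.2 so that EP-attributed toxicity managed without an EP delay has one instruction.

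The cost is an amendment and a letter to sites. Design, sample size and planned precision do not change.
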